1.2 Rationale

This study will show that many patients currently selected for lumpectomy will have better aesthetic outcomes when mastectomy with reconstruction is chosen. While the absolute dimensions of a breast cancer are relevant to staging and treatment, tumor: breast ratio is a key factor in determining patient satisfaction with lumpectomy, and in turn should determine when a mastectomy with reconstruction should be performed to yield an optimal result. It is the relative size of the tumor and volume of its resection that will profoundly impact breast symmetry and therefore impact patient reported outcomes following BCT. Tumor: breast ratios > 0.2 will be associated with progressively poorer patient satisfaction outcomes when treated with BCT than would be provided by mastectomy with reconstruction. Tumors in the superomedial breast will be even more sensitive to tumor: breast ratio. We hypothesize that BCT will be particularly sensitive to tumor: breast ratio whereas mastectomy with reconstruction will be less dependent. The results from this study will enable plastic and oncologic surgeons to identify a new cohort of patients, previously destined for BCT, to undergo a mastectomy with reconstruction to optimize their overall satisfaction with the aesthetic outcomes with equivalent treatment of their disease.

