2.0 OBJECTIVES

2.1 Primary Objective

- At which tumor: breast ratio do patient reported outcomes justify performance of a mastectomy with reconstruction versus BCT in stage-matched patients?

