10.4 Sample Size

Mammometrics will be converted to comparable data and then related to Q-Score as these are expected to be complex relationships.

We anticipate enrolling 83 subjects per study arm (166 total) with up to an additional 20 subjects undergoing mastectomy without reconstruction as a negative control for a total of 186 patients.

Initial plan is to use G*Power v 3.1, or a comparable statistical package. Based on an effect size $d=0.45$, Type I error $\alpha=0.05$, and power $(1-\beta) =0.8$, normal distribution, and 2-tails, we will require 83 subjects per arm (166 total). Assumptions: A difference in mean scores of 10 on a 100-point scale (Q-Score generated from Breast Q) was assumed to be significant. This is determined by assuming an SD of 20, with one-half of an SD being the threshold of discrimination for change in health-related quality of life.

Sample size calculations are based on 1) previously reported sample size calculations where data from the Breast Q for Breast Reconstruction was used with 2) the open-source statistical package G*Power 3.1.

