10.5 Data Analysis

This is a longitudinal observational study to compare effects of two treatment groups on the quality of life and to explore how the treatment effects are modified by T:B ratio. For each study patient, we have a data vector $D=(\text{group}, \text{T:B ratio}, \text{location}, Q(t), 3D(t), W)$, where group is a binary indicator for two comparison groups. T:B ratio is the tumor: breast ratio measured at a continuous scale, and location is a binary indicator of tumor location. $Q(t)$ and $3D(t)$ are Q score and the VECTRA 3D generated mammometrics respectively, measured as continuous variables at $t=(0,1,2)$, where $t=0$ is the pre-treatment baseline measurement. W is a set of patient characteristics – e.g., age, obesity, stage, etc. A longitudinal study generates correlations among the repeated measurements within the same individual, and observational study often comes with a biased estimate of the treatment comparison due to confounding. These two issues, the correlation of repeated measurements and confounding, must be taken into account in the data

analysis. Regression analyses of correlated data can simultaneously address these two issues. There are two families of statistical methods for regression analyses of correlated data – mixed effect model and generalized estimating equation (GEE). Both are appropriate for our study, even though the interpretations are different – population average vs subject specific. Data analyses for our study will be performed within this framework to adjust for the patient characteristics for unbiased comparison of treatment effect and to take into account the correlations.

10.5.1 Primary objectives:

For main effect of treatment group on Q-score: fit and test a model with Q score as the dependent variable and group as the independent variable, controlling for W in the model – (Model 1).

For the difference in Q score between two treatment groups modified by T:B ratio: fit and test a model with Q score as the dependent variable, and group, T:B ratio, and group-by-T:B ratio interaction as the independent variables, controlling for W in the model – (Model 2). The results can be better presented as a graph with two lines – Q score as a function of T:B ratio for those treated with BCT, and for those treated with Mastectomy+reconstruction.

10.5.2 Secondary objectives:

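### Section 10.5.1 does not say how the T:B ratio asked for in objective 2.1 will be obtained from Model 2, against what margin, or with what uncertainty

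*Combined protocol and SAP*

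**What the plan says.** Section 2.1 states one primary objective: "At which tumor: breast ratio do patient reported outcomes justify performance of a mastectomy with reconstruction versus BCT in stage-matched patients". The answer has to be a value, or a range of values, of the T:B ratio.

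Section 10.5.1 assigns two models to it. Model 1 tests the main effect of group on the Q-score. Model 2 has "group, T:B ratio, and group-by-T:B ratio interaction as the independent variables, controlling for W in the model". On output it adds "The results can be better presented as a graph with two lines", one line per treatment group, with Q-score as a function of T:B ratio. It gives no definition of the target ratio, no margin, no interval for a ratio and no rule for concluding that one was or was not found.

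Two figures that could bear on the question stand elsewhere and are not carried into section 10.5:

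- Section 10.4: "A difference in mean scores of 10 on a 100-point scale (Q-Score generated from Breast Q) was assumed to be significant", derived by "assuming an SD of 20, with one-half of an SD being the threshold of discrimination for change in health-related quality of life".
- Section 1.2: "Tumor: breast ratios > 0.2 will be associated with progressively poorer patient satisfaction outcomes when treated with BCT".

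Section 10.5 also says that the Q-score is measured at three times, the first being the pre-treatment baseline. Model 2 as written has no visit term.

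**The concern.** The plan holds a question (at what ratio?) and a possible yardstick for a difference that matters (10 points), but does not connect them. Followed as written, it ends with two p-values and a picture. Neither p-value is a ratio. The picture lets a reader choose a ratio after the data are seen, by whatever criterion looks natural, with no statement of uncertainty.

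This matters because section 1.2 intends the result to identify women who would now have BCT and would instead be offered mastectomy with reconstruction. A ratio put to that use needs a definition fixed in advance and an interval. There is also a risk of over-reading: the interaction can be significant although the advantage never reaches a meaningful size in the observed range, and the primary question would then seem answered when it is not.

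**Working it through.** **Sample size in section 10.4.** Inputs: d = 0.45, two-sided alpha 0.05, power 0.80. The normal approximation gives 78 per arm and the t-test 79. A Wilcoxon-Mann-Whitney test with a normal parent distribution (efficiency 3/π = 0.955; 83 × 0.955 = 79.3) gives 83 per arm with power 0.804, which is the stated figure. It is sized for a two-group comparison of Q-scores. T:B does not enter it.

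**The 10 points and d = 0.45 do not agree.** With SD 20, 10 points is d = 10/20 = 0.50, while d = 0.45 is 0.45 × 20 = 9 points. Keeping 10 points and d = 0.45 would need an SD of 10/0.45 = 22.2. At d = 0.50 the Wilcoxon-Mann-Whitney calculation needs 67 per arm, so 83 is not too few for the group comparison. The conflict matters here because it leaves the margin unsettled.

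**What Model 2 implies.** Let D(r) be the adjusted difference (mastectomy + reconstruction minus BCT) at T:B ratio r, with D(r) = a + b·r.

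- Crossing of the lines: D = 0 at r0 = −a/b.
- Margin m reached: D = m at rm = (m − a)/b.
- Distance between them: rm − r0 = m/b.

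The interaction test concerns b alone. The ratio depends on a and b together, and its uncertainty on their joint distribution.

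**Size.** The documents give no b, so the slopes below are assumptions. The last column also assumes a crossing at the 0.2 named in section 1.2.

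| b (points per unit T:B) | 10/b | 9/b | 10-point ratio if the crossing is 0.20 |
|---|---|---|---|
| 50 | 0.20 | 0.18 | 0.40 |
| 100 | 0.10 | 0.09 | 0.30 |
| 200 | 0.05 | 0.045 | 0.25 |

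With b = 50 and a crossing at 0.20, the difference at r = 0.35 is 50 × 0.15 = 7.5 points. If the observed ratios stopped there, a real interaction would exist and 10 points would never be reached.

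**Precision, by illustrative simulation.** All inputs are assumed: 83 per group, residual SD 20, gamma-distributed T:B with mean 0.15, true crossing 0.20, one post-operative score, no covariates, 4,000 replicates. With T:B SD 0.10:

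| b | Interaction significant | Estimated crossing, central 95% | Estimated 10-point ratio, central 95% (true value) |
|---|---|---|---|
| 50 | 35% | −0.26 to 0.68 | −1.59 to 2.26 (0.40) |
| 100 | 87% | 0.14 to 0.33 | 0.22 to 0.58 (0.30) |
| 200 | 100% | 0.17 to 0.24 | 0.21 to 0.31 (0.25) |

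With T:B SD 0.05, the interaction was significant in about 12%, 35% and 88% of replicates for the same slopes. A 95% Fieller interval is bounded only when b differs significantly from zero, so these percentages are also how often a bounded interval would result. Two lines without a band need not reveal any of this.

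**The case against.** The strongest reply is that the plan nowhere adopts the crossing. Section 10.5.1 only suggests a display, and that display shows the vertical gap at every T:B value, so a 10-point gap can be read from it as easily as a zero gap. Section 10.5 also describes the aim as exploring how T:B modifies the treatment effect, and the coefficients needed for any threshold will be estimated.

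Most of this stands. A reader might infer that the plan uses a zero-difference rule, that the crossing is the only value the graph offers, or that the reported ratio will be too low. The documents support none of these. No rule is stated, so no reported ratio can yet be called too low. Section 1.2 is worded directionally and gives no margin.

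A reader might also take 10 points as the protocol's settled criterion for preferring one operation. It is a sample-size assumption, supported by a half-SD threshold for change in quality of life. It is not carried over to a between-group difference at a given T:B ratio, and it conflicts with d = 0.45.

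What the reply does not remove is the gap. Model 2 is the only model under the primary heading that contains T:B, and the plan does not say how it answers the question in section 2.1. Reading a gap by eye is not an estimate with an interval, and choosing the gap afterwards is not prespecification.

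**Conclusion.** The point holds as an undefined target. Section 10.5.1 does not say how the ratio in objective 2.1 is derived, against what margin, or with what uncertainty. This follows from the text alone and needs no assumption.

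The size is conditional. Zero and a 10-point margin are separated by 10/b on the T:B scale, that is 0.05 to 0.20 for assumed slopes of 200 down to 50 points per unit. These distances are a quarter to the whole of the 0.2 ratio in section 1.2, but no slope, T:B distribution or crossing is documented, so they show only that the choice of margin can matter. The simulated ranges depend on assumptions in the same way. They show that the ratio may be poorly determined at 83 per arm, which is a reason to plan an interval.

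This should be changed before analysis. It does not invalidate the design.

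**What to change.** In section 10.5.1:

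1. Specify the visit in Model 2, so that the group-by-T:B contrast is estimated at the final visit and not pooled with the baseline. Name the Breast-Q domain, since section 6.1 lists several.
2. Plot the adjusted difference (mastectomy + reconstruction minus BCT) against T:B with its 95% confidence band and reference lines at zero and at a prespecified margin.
3. Report the T:B ratios at which the difference reaches zero and the margin, each with a 95% interval by Fieller's method or bootstrap, restricted to the T:B range seen in both groups.
4. Have the sponsor set and justify the margin in advance, starting from the 10 points in section 10.4 after reconciling them with d = 0.45 (9 points at SD 20). The margin is a statistical target for reporting, not a rule for choosing surgery.
5. State whether the point estimate or its confidence limit must reach the margin. If it is not reached within the shared range, state that no such ratio was shown.

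The cost is SAP wording, a visit term with its interactions, and functions of the fitted coefficients. No new data are needed. The downside is that the interval may be wide or unbounded, and the report would then have to say that the data do not locate a ratio.

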2.2 Secondary Objectives

- Does tumor location impact the influence of tumor: breast ratio on patient reported outcomes following mastectomy with reconstruction or BCT?
- How does the pre and post-op Breast Q for the two groups (mastectomy + recon vs. BCT) reflect the tumor: breast ratio as calculated from 3D images rendered from MRI utilizing software-based algorithms?
- How does the pre and post-op Breast Q for the two groups (mastectomy + recon vs. BCT) reflect the VECTRA 3D generated mammometrics?

- What is the impact of radiation in BCT on Breast Q (Q-score before and after radiotherapy) and VECTRA (breast volume, nipple position, total breast skin surface area before and after radiotherapy)?
- How do complications that arise from each scenario (mastectomy + recon) vs. BCT impact patient satisfaction?
- What is the impact of tumor location and obesity as independent determinants of patient satisfaction in the two groups (mastectomy + recon vs. BCT) relative to tumor: breast ratio?

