8.0 DATA SUBMISSION SCHEDULE

Case Report Form	Submission Schedule
Original Consent Form	Prior to registration
Eligibility Checklist RedCap Enrollment, Visit 1, Visit 2 MRI, and Visit 3 Plastics (if applicable)	Prior to surgery
RedCap Surgical Intervention	Following receipt of final operative and pathology reports
RedCap Follow-Up Forms Post-Operative Visit 1, Oncology Course, and Post-Operative Visit 2	
Group A:
 
 ○ Post-Lumpectomy 1st post-op visit before Radiotherapy (1-10 weeks after lumpectomy) ○ Post-Lumpectomy post-op visit after radiotherapy (6-18 months after radiation or the latest follow-up time point within the duration confines of our study period.) 
Group B:
 
 ○ Post-mastectomy 1st post-op visit before completion of reconstruction (1-10 weeks after mastectomy) ○ Post-mastectomy Post-op Visit after final reconstruction (3-8 months after final reconstructive procedure or the latest follow-up time point within the duration confines of our study period.) 
Group C:
 
 ○ Post-mastectomy 1st post-op visit (1-10 weeks after mastectomy) Post-mastectomy post-op visit (6-18 months after mastectomy or the latest follow-up time point within the

	duration confines of our study period.)
Unanticipated Event via HRPO	At the time of any unanticipated event
MRI T:B ratio, Breast Q-Scores, and Vectra Mammometrics	The coordinators will ensure MRI performed, Breast-Q's completed and Vectra images captured during active patient phase. MRI T:B ratio will be performed late in the active study phase to allow for a limited number of staff to perform bulk of measurements to optimize standardization. There is also a possibility the software will be upgraded to automate the T:B ratio later in the study period. Breast-Q scores and Vectra mammometrics will be also evaluated in bulk late in the active study phase using SAS, SPSS, or another similar statistical program.

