Does tumor location impact the influence of tumor: breast ratio on patient reported outcomes following mastectomy with reconstruction or BCT?

- Add location and three way interaction term –group-by-T:B ratio-by-location into Model 2 – (Model 3). The results can be better presented as two graphs – one for each location. See Model 2 for the graph.

How does the pre and post-op Breast Q for the two groups (mastectomy + recon vs. BCT) reflect the tumor: breast ratio as calculated from 3D images rendered from MRI utilizing software-based algorithms?

- Fit and test a model with Q-score as the dependent variable and 3D image data as the independent variable with appropriate non-linear terms for 3D (e.g. spline functions), with group and possible interaction of group-by-3D (Model 4).

How does the pre and post-op Breast Q for the two groups (mastectomy + recon vs. BCT) reflect the VECTRA 3D generated mammometrics?

- Both the Breast Q and the VECTRA 3 D generated mammometrics are continuous variables. The correlation between them will be quantified by Pearson or Spearman correlation coefficient with one sample t test for population correlation coefficient =0, and with Fisher Z transformation to test the population correlation coefficient not equal to zero.

What is the impact of radiation in BCT on Breast Q (Q-score before and after

radiotherapy) and VECTRA (breast volume, nipple position, total breast skin surface area before and after radiotherapy)?

- Perform the subgroup analyses of BCT patients comparing change in outcomes of interest before and after radiation.

How do complications that arise from each scenario (mastectomy + recon) vs. BCT impact patient satisfaction?

- Fit and test a model with Q-score as the dependent variable and complication and group, and possible group-by-complication interaction as independent variables controlling for W in the model.

What is the impact of tumor location and obesity as independent determinants of patient satisfaction in the two groups (mastectomy + recon vs. BCT) relative to tumor: breast ratio?

- Fit and test a model with Q-score as the dependent variable and group, T:B ratio, location, and obesity as the independent variables, controlling for W in the model. Obtain the standardized regression coefficients for location, obesity, and T:B ratio, and compare each other to determine their relative importance.

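### Model 3 omits group-by-location and T:B-by-location, so with 0/1 indicators its answer on tumor location can depend on which group is coded 1

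*Combined protocol and SAP*

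**What the plan says.** Section 10.5 defines the variables: "group is a binary indicator for two comparison groups", "location is a binary indicator of tumor location", and "T:B ratio is the tumor: breast ratio measured at a continuous scale". Model 2, in Section 10.5.1, has "group, T:B ratio, and group-by-T:B ratio interaction as the independent variables, controlling for W in the model". Model 3, in Section 10.5.2, is specified as an addition to it: "Add location and three way interaction term –group-by-T:B ratio-by-location into Model 2". It is meant to answer the first question of Section 2.2: "Does tumor location impact the influence of tumor: breast ratio on patient reported outcomes following mastectomy with reconstruction or BCT". The results are to be shown as one graph per location, each in the style of the Model 2 graph with a line for each group.

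Section 1.2 gives the expectation: "Tumors in the superomedial breast will be even more sensitive to tumor: breast ratio". The same section expects BCT to depend on the ratio more than mastectomy with reconstruction does.

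The plan does not say that lower-order terms are included, which group is coded 1, whether the T:B ratio is centred, or which test answers the question. The one statement about software, in Section 8.0, leaves the program open: "using SAS, SPSS, or another similar statistical program".

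**The concern.** A three-way product is normally fitted together with all three of its two-way products. Here only group-by-T:B is present, carried over from Model 2. T:B-by-location is the term that lets location change the T:B slope in the reference group. Group-by-location is the term that lets the group difference vary by location for reasons unrelated to the slope. Without them, the three-way coefficient takes on work that is not its own, and its meaning depends on an arbitrary choice of reference group.

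At stake is the answer to the first secondary objective. Two analysts could follow the text faithfully, code group in opposite ways, and report different conclusions from the same data.

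**Working it through.** **Inputs.** From Section 10.4: 83 per arm, SD 20, two-sided 0.05. The figure of 83 can be reproduced at d = 0.45. The normal formula gives 2(1.960 + 0.842)²/0.45² = 77.5, so 78, and the t-test gives 79. Allowing for a Wilcoxon–Mann–Whitney test with a normal parent distribution gives 79/(3/π) = 79/0.955 = 82.7, so 83. The plan gives no sample size for Model 3.

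**Step 1, algebra.** Write G for group, T for T:B ratio and L for location, and leave W aside. The listed model is

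E[Q] = b0 + b1·G + b2·T + b3·G·T + b4·L + b5·G·T·L.

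- T:B slope when G = 0: b2 in both locations.
- T:B slope when G = 1: b2 + b3 + b5·L.
- Group difference at T = 0: b1 in both locations.

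Replacing G by 1 − G turns the last product into (1 − G)·T·L = T·L − G·T·L, and T·L is not in the model. The recoded model is therefore a different one. This needs no assumed effect size.

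**Step 2, rank check.** The design matrices for the two group codings each have rank 6, and placed side by side they have rank 7, whether or not T is centred. Flipping the location code leaves the rank at 6, so only the group code matters. With the two missing terms added, the rank is 8 and stays 8 under recoding.

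**Step 3, noise-free example.** Assume T uniform on 0–0.5, BCT slopes −20 (other locations) and −60 (superomedial), and slopes of 0 after mastectomy with reconstruction. With BCT coded 1, the listed model returns these slopes exactly. With BCT coded 0, it returns −40 and −40 for BCT and about −12 and +12 for mastectomy with reconstruction: the location effect appears in the wrong group. The full model returns the true slopes.

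**Step 4, how often the codings disagree.** Least-squares simulation with 83 per arm and SD 20. Assumed, not in the documents: 30% superomedial, one score per patient, no W, the T:B distributions below (lognormal with log-SD 0.7), and a location effect on the slope in BCT only. The effect at ratio 0.2 is the slope times 0.2.

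| Slope effect per unit T:B | Effect at ratio 0.2 | T:B distribution | Codings disagree |
|---|---|---|---|
| none | 0 | any of these | about 8% |
| 50 | 10 points | lognormal, median 0.04 | about 10% |
| 50 | 10 points | lognormal, median 0.08 | about 18% |
| 25 | 5 points | uniform 0–0.4 | about 15% |
| 50 | 10 points | uniform 0–0.4 | about 33% |
| 125 | 25 points | lognormal, median 0.08 | about 50% |

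In the last case the three-way term is significant in 24% of runs with mastectomy coded 1 and 72% with BCT coded 1. Centring T does not cure this: 5% against 43%, with disagreement in 44%.

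**Step 5, missing group-by-location.** Take no slope effect but a 10-point group-by-location shift. With uncentred T, the listed three-way term is significant in about 14–21% of runs at a nominal 5%. At a 5-point shift the rate is about 8%. With centred T it is about 5%, and the full model's three-way term stays at 4–6%.

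**Step 6, an effect shared by both groups.** At 125 points per unit in both groups (median 0.08), the listed three-way term is significant in about 28% of runs uncentred and 46% centred. In the full model, the joint 2-df test of T:B-by-location and the three-way term is significant in about 64%, and the three-way term alone in 5%.

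**The case against.** The strongest reply is that the full model was meant. Two graphs with a line per group suggest four free slopes, and naming only the highest-order term can be shorthand. That may be the intention, but the text lists what to add and names the location main effect. Model 2 also spells out its lower-order terms, so the two absent ones are not plainly implied.

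A second reply is that software can fill the gap. If group and location are entered as class variables, a program may expand the three-way term into a separate location slope for each group. That removes the coding dependence and gives a suitable 2-df test. This stands, but group-by-location is still missing, and the plan does not require that form of entry.

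Third, the false-signal result in Step 5 needs a location shift that persists at a ratio of zero, where there is no tumor volume, and it vanishes with centring. It is a lesser part of the point.

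Two stronger readings are tempting. A reader might infer that the listed three-way term is blind to a location effect common to both groups. It is not: it detects one in about 28–46% of runs in Step 6, and the 5% belongs to the three-way term of the full model. A reader might also infer that about half of all analyses would flip with the coding. That needs 125 points per unit ratio, or 25 points at a ratio of 0.2, and nothing in the documents supports an effect of that size.

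**Conclusion.** As written, Model 3 is incomplete. With 0/1 indicators it gives a coding-dependent answer, and this part is exact. If BCT is coded 0, the effect that Section 1.2 leads one to expect in BCT cannot be fitted.

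The practical size is uncertain. For a BCT-only effect, disagreement between codings runs from about 10%, close to the 8% seen with no effect, to about 50%. Where it falls depends on the slope and the T:B distribution, neither of which the documents give. Using several scores per patient or adding W does not change the picture. At 125 points per unit and median 0.08, disagreement is 40–49% with the mean of three scores and the effect present only after surgery, and 54% with three covariates.

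The fault is confined to one secondary objective of an observational study. The documents give no ground for extending it to the primary analysis, because Models 1 and 2 contain no location interaction.

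**What to change.** Write Model 3 with group, T:B ratio, location, group-by-T:B, group-by-location, T:B-by-location and the three-way term, plus W. Then state:

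- The secondary question is answered by the joint 2-df test of T:B-by-location and the three-way term.
- The three-way term is reported separately, as the test of whether the location effect on the slope differs between groups. It should not answer the question alone, since it does not respond to an effect shared by both groups.
- The location difference in T:B slope is given within each group with a 95% CI, so that the reader sees in which group location matters.
- The coding of group and location and any centring of the T:B ratio are stated. In the full model neither affects the two tests above.
- Power for this objective is low.

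The change is to wording only and needs no new data. It adds two parameters (6 to 8 columns before W). Power is lower than under a coding that happens to match the truth: in the 125-point BCT-only case it falls from 72% to about 37% for the joint test and about 25% for the three-way term. The opposite coding of the listed model gives 24% in that case and places the effect in the wrong group. In the uniform case at 50 points per unit, the joint test has about 16% power, which is why the limitation should be stated.

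### The Breast-Q versus VECTRA objective is given only a correlation test, with no visit, arm, covariate or within-patient term stated

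*Combined protocol and SAP*

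**What the plan says.** Section 2.2 lists the objective, and section 10.5.2 repeats it: "How does the pre and post-op Breast Q for the two groups (mastectomy + recon vs. BCT) reflect the VECTRA 3D generated mammometrics". The analysis under it is brief. It notes that both measures are continuous and then says: "The correlation between them will be quantified by Pearson or Spearman correlation coefficient". A t test of zero correlation and a Fisher Z transformation are attached to that coefficient. No visit, treatment group, covariate or patient effect is mentioned.

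The general part of section 10.5 defines both the Q-score and the VECTRA mammometrics, written Q(t) and 3D(t), at a pre-treatment baseline and two later times. W is the set of patient characteristics, with age, obesity and stage as examples. On how the analysis is to treat repeated measurement and confounding, it says: "These two issues, the correlation of repeated measurements and confounding, must be taken into account in the data". It names mixed models and GEE as suitable and adds: "Data analyses for our study will be performed within this framework to adjust for the patient characteristics".

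Three neighbouring items in the plan matter here:

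- The complications analysis and the location/obesity analysis in section 10.5.2 both state adjustment for W.
- Model 4 in section 10.5.2 regresses Q-score on 3D image data with non-linear terms, group and a possible group-by-3D interaction. It is assigned to the MRI tumor:breast ratio objective and does not mention W or visit.
- Section 10.4 expects the relation between mammometrics and Q-score to be complex.

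**The concern.** The question has a time dimension (before and after surgery) and a group dimension (two operations). The stated analysis has neither. The usual tests of a Pearson or Spearman coefficient assume independent pairs, and a simple coefficient has no means of adjustment. Three distinct things can go wrong, depending on how the sentence is carried out:

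1. **Visits pooled.** Each patient supplies up to three pairs. If both measures are correlated within patient, the test overstates the information and its p-value is too small.
2. **Arms pooled.** If the operations differ in both Q-score and breast shape, a correlation appears across arms even when there is none within either arm.
3. **Any reading.** A patient characteristic related to both measures creates or hides a correlation. Obesity, which the plan places in W, is a plausible candidate.

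What is at stake is a claim that VECTRA measurements track patient satisfaction, when the signal may come from repeated counting, type of operation or patient mix.

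**Working it through.** **The plan's own figure.** The documents give no sample size, power or detectable correlation for this objective. The only related figure is 83 per arm in section 10.4 (d = 0.45, two-sided 0.05, power 0.80). The normal formula gives 78 per arm and the noncentral t gives 79. The Wilcoxon-Mann-Whitney version with a normal parent (efficiency 3/π) gives 83, with power 0.804. The 83 is therefore reproducible and is used below only as the sample size.

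**Inputs from the plan:** 83 per arm, 166 in the two compared arms, three visits (166 × 3 = 498 pairs), α = 0.05 two-sided, d = 0.45 for Q.

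**Inputs assumed, because the documents give none:** within-patient correlation (ICC) 0.3 to 0.7 in both measures; VECTRA arm difference 0.25 to 1.0 SD; one confounder correlated 0.3 to 0.5 with each measure. In every case Q and VECTRA are unrelated once arm, visit and confounder are held fixed. Simulations used 4,000 trials per scenario.

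**Reading 1: three visits pooled, no arm difference, no confounder.** Design effect = 1 + 2 × ICC². Type I error = 2 × [1 − Φ(1.96/√design effect)].

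| ICC | Design effect | Effective pairs of 498 | Formula | Simulation |
|---|---|---|---|---|
| 0.3 | 1.18 | 422 | 7.1% | 7.8% |
| 0.5 | 1.50 | 332 | 11.0% | 10.5% |
| 0.7 | 1.98 | 252 | 16.4% | 16.3% |

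Spearman behaves similarly. This is true type I error inflation.

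**Reading 2: one post-operative visit, both arms pooled (n = 166).** With arm differences d₁ in Q and d₂ in VECTRA, in within-arm SDs and with equal arms, the marginal correlation is r = (d₁d₂/4) / √[(1 + d₁²/4)(1 + d₂²/4)]. The chance of significance follows from Fisher Z with mean atanh(r) × √163.

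| d₁ | d₂ | r | Formula | Simulation |
|---|---|---|---|---|
| 0.45 | 0.25 | 0.027 | 6.4% | 6.4% |
| 0.45 | 0.5 | 0.053 | 10.4% | 9.7% |
| 0.45 | 1.0 | 0.098 | 24.2% | 24.0% |

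Section 10.4 also gives a 10-point difference on an SD of 20, which is d₁ = 10/20 = 0.50. Using that changes the last two rows of the formula column to 11.7% and 28.5%.

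**Reading 3: one visit within one arm (n = 83).** With no confounder, simulated rejection is 4.6% to 5.7%, so the clustering and arm problems are gone. A confounder correlated c with both measures induces r = c², and the Fisher Z mean is atanh(c²) × √80.

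| c | r = c² | Formula | Simulation |
|---|---|---|---|
| 0.3 | 0.09 | 12.7% | 12.5% |
| 0.4 | 0.16 | 30.3% | 29.1% |
| 0.5 | 0.25 | 62.7% | 63.2% |

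If the confounder acts in opposite directions on the two measures, r is negative and a real positive association can be masked.

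**After the fix.** An analysis centred by arm and visit, adjusted for the confounder and with patient-clustered standard errors, rejects 4.6% to 5.4% of the time in these scenarios.

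**The case against.** The strongest defence is that the sentence is brief rather than wrong. The objective names pre- and post-operative scores and two groups, so separate correlations by visit and by group are a natural reading. On that reading there is no clustering or arm problem. This stands as a limit: a reader might infer that the plan pools all visits and arms, but the text does not say so. It does not say the opposite either, and confounding remains in both cases.

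A reader might also call the arm-pooled rates type I error, or quote a rate near 75%. Neither is supported. The stated null is zero population correlation. If arms differ in both measures, the marginal correlation is truly non-zero: 0.0625/1.0625 = 0.059 at 0.5 SD in both, and 0.25/1.25 = 0.20 at 1.0 SD in both. Rejecting that null is correct; the error lies in reading the result as a within-arm association. The same holds for the confounder figures. A rate near 75% needs 1.0 SD in both measures, which is 20 Q-score points at the plan's SD of 20, or twice its 10-point threshold.

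Section 10.5 introduces confounding as a bias in the treatment comparison, and this objective is not one. That softens the conflict with the plan's own rule. It does not remove it, because the sentence requiring both issues to be handled is general and the repeated-measures part applies to any longitudinal analysis here.

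The sponsor could call the correlation descriptive, but hypothesis tests are specified. It could point to Model 4, which has most of the right form, but Model 4 belongs to another objective and omits W and visit.

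**Conclusion.** The point holds in a limited form. A hypothesis test is specified for a longitudinal, two-group question without stating the unit of analysis and without any visit, arm, W or within-patient term. This sits badly with section 10.5.

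The size depends on the reading:

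- about 7-8% to 17% type I error if visits are pooled;
- about 6-24% significance from arm differences alone if arms are pooled at one visit;
- about 13-63% significance from confounding alone if the test is run by arm and visit.

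All of these rest on assumed within-patient correlations, VECTRA arm differences and confounder strengths, and the direction of confounding is unknown. The documents do not support saying that the test will produce false associations, only that it cannot separate a within-arm association from these other sources. This is one of six secondary objectives, and the primary analysis is unaffected.

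**What to change.** Extend Model 4 to the VECTRA objective. Regress Q(t) on 3D(t), with spline terms where needed, together with visit, group, group-by-3D and W, using a patient random effect or GEE. Report the association within each arm with its confidence interval. Keep Pearson or Spearman coefficients as descriptive figures by arm and by visit, without tests. State the unit of analysis explicitly.

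The cost is a few lines of SAP wording and slightly more analysis. No new data are needed, since Q(t), 3D(t), group and W are already in the plan's data vector.
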